- a) History of major psychiatric illness*
- b) Actively using a neuropsychoactive medication*
- c) Legal or mental incompetency*
- d) Substance use disorder, abuse or dependence, with active use within the last 3 months*
- e) Significant medical or neurological illness*
- f) Prior neurosurgical procedure*
- g) History of seizure*
- h) History of ECT or TMS treatment within the past three months*
- i) Presence of a pacemaker, implanted medical pump or device, metal plate, or metal object in skull or eye (including shunts, dental implants, facial tattoos with metallic ink)*
- j) Pregnant women*

4.3. This study will not include any participants from any special populations (adults unable to consent, children, pregnant women, or prisoners).

4.4. This study will exclude pregnant women and children (due to safety and potential risk), prisoners and those who cannot competently provide their own consent (due to these groups being special populations) and will also exclude those who do not fluently speak or understand English (as our consent will be in English and study team members are fluent in English).

PROTOCOL TITLE: *Metaplasticity in the human motor cortex: validation of an experimental design and comparison of motor outcome measure sensitivity to change*

5. Number of Subjects

- 5.1. *This is not a multisite study and will only recruit subjects at this site.*
- 5.2. *We will aim to recruit 16 subjects for this study.*
- 5.3. *Sixteen subjects will be enrolled for this study according to the MANOVA model (anodal, cathodal, and sham) and a specified number of variables (time points—M1-M4) at the significance level of $\alpha=0.05$ and 80% power to correspond to the very large effect size. We have based the calculation on the very large effect size as seen in Quartarone et al., 2005. The desired sample size was found to be 16 patients per treatment arm. We will fulfill this sample size requirement with a crossover design as all 16 subjects will participate in each treatment arm. We would request a recruitment ceiling of 20 subjects to account for subject dropout and if a subject were to meet exclusion criteria after signing the consent.*

6. Study Timelines

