- **M4** (10 minutes post-rTMS measurement): neurophysiological outcome assessment (MEP, CSP) and behavioral outcome (reaction time task)

13. Data Analysis

13.1. Aim 1: To compare pre- and post- measures of cortical excitability after inhibitory and excitatory priming of the motor cortex. Hypothesis 1: We expect priming tDCS to affect the response to rTMS, namely we expect “inhibitory” cathodal tDCS to cause a reversal of the normal inhibitory effect of 1Hz rTMS. Hypothesis 2: We expect “excitatory” anodal tDCS to have no effect on the normal inhibitory effect of 1Hz rTMS. Hypothesis 3: We expect sham tDCS to have no effect on the normal inhibitory effect of 1Hz rTMS. We will use a MANOVA model (anodal, cathodal, and sham) and a specified number of

PROTOCOL TITLE: *Metaplasticity in the human motor cortex: validation of an experimental design and comparison of motor outcome measure sensitivity to change*

variables (time points—M1-M4). MANOVA assumes normality of the residuals and equality of variance across groups. In the case of violation of these assumptions, we will explore data transformations, including logarithmic, power, and inverse-normal transformations, to identify an analytic scale under which modeling assumptions are met. Should transformations not be adequate, we will employ non-parametric methods instead.

Exploratory Aim 2: To evaluate the sensitivity of motor outcome measures to changes in cortical plasticity. Hypothesis 1: We expect different measures of motor cortex excitability to be more sensitive than others at detecting changes in cortical excitability. We will be comparing in an exploratory but systematic fashion various measures of motor cortex excitability (e.g. peak-to-peak amplitude change in motor evoked potential (MEP) and the integrated area of the MEP (root mean square)) with the cortical silent period (CSP) and behavioral measures (reaction time). We will perform both a linear regression as well as a Principal Components Analysis (PCA) to identify which cortical excitability factors are most sensitive to change due to noninvasive neurostimulation.

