13.2. *Power analysis:* Sixteen subjects will be enrolled for this study according to the MANOVA model (anodal, cathodal, and sham) and a specified number of variables (time points—M1-M4) at the significance level of $\alpha=0.05$ and 80% power to correspond to the very large effect size. We have based the calculation on the very large effect size as seen in Quartarone et al., 2005. The desired sample size was found to be 16 patients per treatment arm. We will fulfill this sample size requirement through a crossover trial as all 16 subjects will participate in each treatment arm. We would request a recruitment ceiling of 20 subjects to account for subject dropout and if a subject were to meet exclusion criteria after signing the consent.

14. Provisions to Monitor the Data to Ensure the Safety of Subjects

14.1. The PIs will consist of the medical monitoring team for this study due to its minimal risk status.

14.2. We will collect data on the safety of rTMS including expected side effects: headache (expected 17% with transient headache that responds to simple analgesic) and nonspecific feelings of discomfort. We will collect data on rare but serious adverse events such as seizures (reported at 1.4%).

14.3. The safety data will be reviewed on an ongoing basis during enrollment and conduct of the study.

14.4. We plan to follow the most recent safety recommendations from expert consensus panels on rTMS.

14.5. We have no planned formal analysis of the safety data.

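### The sample size is stated per arm and filled with the same 16 people, and neither the planned MANOVA nor the 80% power is tied to a within-participant test

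*Combined protocol and SAP*

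**What the plan says.** Section 3.1 describes a randomized three-visit crossover, so 16 people give 48 sessions.

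Section 13.2 sizes it as follows: "Sixteen subjects will be enrolled for this study according to the MANOVA model (anodal, cathodal, and sham) and a specified number of variables", the variables being the four time points. Alpha is 0.05, with "80% power to correspond to the very large effect size". The effect is taken from a cited earlier study and no number is given. The result is a per-arm figure, met by reusing the same people: "The desired sample size was found to be 16 patients per treatment arm. We will fulfill this sample size requirement through a crossover trial". Section 5.3 says the same: "We will fulfill this sample size requirement with a crossover design as all 16 subjects will participate in each treatment arm". On losses, 13.2 adds: "We would request a recruitment ceiling of 20 subjects to account for subject dropout".

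For the Aim 1 analysis, 13.1 says "We will use a MANOVA model (anodal, cathodal, and sham"), again with M1 to M4 as the variables. The assumptions listed are normal residuals and equal variances; dependence between one person's visits is not mentioned. If transformation fails: "Should transformations not be adequate, we will employ non-parametric methods instead". Those methods are not said to be paired.

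**The concern.** In a crossover, condition is compared within a person. A one-way MANOVA on condition uses the spread between people as its error, so it does not credit the design for removing that spread. The per-arm figure and the analysis are both worded as though the arms held different people.

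Two things are at stake. The literal test would run below its nominal 5% and could give away power that the crossover was chosen to provide. And the stated 80% cannot be attached to any particular test, because the test, the numeric effect and the between-visit correlation are all missing. In a study meant to validate a method, the choice of primary test should not be left until the data are in.

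**Working it through.** **1. Reproducing the 16.** This cannot be done from the documents, because the effect is only a label. As an illustration, take three independent groups and four variables, with the extreme groups an assumed 1.5 SD apart (multivariate distance) and the third midway. The number per group for 80% power is then 16 by Wilks (80.4%), 15 by Hotelling-Lawley and 18 by Pillai. Over assumed distances of 1.0 to 2.0 SD, it runs from 34 down to 8. So 16 is compatible with an independent-groups calculation but does not establish one.

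**2. Why the literal test is conservative.** At one time point, let the variance be σ² and the between-visit correlation ρ. For two condition means on the same n people:

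- true variance of the difference = 2σ²(1−ρ)/n
- variance used by the literal test = 2σ²/n

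With n = 16, σ² = 1 and ρ = 0.6, these are 2 × 0.4/16 = 0.05 and 2/16 = 0.125. The error term is 2.5 times too large, so the test rejects too rarely.

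**3. Size and power in simulation.** All variance inputs are assumptions, since the plan gives none. Total variance is 1. The shares for participant/session/residual are A 0.6/0.15/0.25, B 0.4/0.2/0.4, C 0.7/0.1/0.2 and D 0.5/0.15/0.25, with a further 0.1 for participant-by-time. The effect is a shift at M3 and M4 of −d in sham and anodal and +d in cathodal, with d = 0.315, 0.389, 0.284 and 0.367 SD. These values give 79.7, 80.1, 79.3 and 79.6% power with 48 separate people. MANOVA rows use Pillai's trace; 20,000 runs.

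| Test, 16 people | Error df | Size %, A/B/C/D | Power %, A/B/C/D |
|---|---|---|---|
| As written, 48 sessions, M1-M4 | 48−3 = 45 | 2.0/2.5/1.9/0.4 | 74/77/74/73 |
| Participant and visit added, M1-M4 | 48−1−15−2−2 = 28 | about 4.4 | 80/80/83/93 |
| Repeated-measures T², (3−1)×(4−1) = 6 contrasts | 16−6 = 10 | 5.0-5.1 | 62/61/63/78 |
| Participant, visit, M1 covariate; M2-M4 | 28−1 = 27 | 4.3-4.5 | 86/85/87/95 |

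**4. Spread among readings the wording allows.** The first three rows keep M1 to M4 as the variables, as the plan does. Highest minus lowest power: A 80−62 = 18, B 80−61 = 19, C 83−63 = 20, D 93−73 = 20 points. The fourth row is not a reading of the plan, so it is left out.

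**5. When visits are weakly correlated.** Take case A's effect and within-session correlation (0.75), let only the person's level repeat, and set ρ = 0/0.2/0.4/0.6:

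- as written: 80/78/77/75%
- participant and visit, M1 covariate: 78/79/81/86%
- participant and visit, M1-M4: 71/72/74/80% (20,000 runs made to check this cost)

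In a second set of assumptions (Wilks, 1.5 SD, correlation repeating across the whole time pattern, participant term only), power as written against blocked is 81 against 77% at ρ = 0 and 79 against 88% at ρ = 0.2. The size of the literal test there is about 5.3% at ρ = 0, 0.8% at 0.3 and 0.1% at 0.5.

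**6. What the omnibus test detects.** Suppose a tDCS after-effect (+d anodal, −d cathodal) persists unchanged from M2 to M4, with the same rTMS effect in every condition. The test as written rejects in 50/57/47/46% of runs (A-D), and the M1-covariate version in 77/77/80/89%. Power for the condition test is therefore not power for Hypothesis 1, which concerns the response to rTMS.

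**The case against.** The power paragraph states the crossover openly. The plan may use MANOVA to mean the multivariate repeated-measures test, in which pairing is built in. Section 3.2 uses the word group loosely for condition, so the mention of groups in 13.1 is weak evidence of an independent-groups analysis. Section 8.3 involves a biostatistics core in the analysis. The trial is a small proof-of-principle study, the literal test errs on the safe side, and every percentage above rests on assumed variances and an assumed effect.

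Most of this stands, and it limits the point to a gap in specification. It does not close the gap. The repeated-measures test is not named, a per-arm number does not describe it, and in cases A to C it gives only 61-63% for the same effect.

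A reader might infer three stronger things. One is that the 80% was calculated for independent groups: the wording suggests this, but the calculation is not shown. Another is that 16 is too few: with participant and visit in the model, 16 people reach 80% or more in all four cases, and other assumptions give less or more. The third is that entering M1 as a response is a mistake: the stated aim is "To compare pre- and post- measures of cortical excitability after inhibitory and excitatory priming of the motor cortex", so it is not.

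**Conclusion.** The point holds as a specification gap that should be fixed, with modest consequences. Run literally, the test has a size of about 0.4-2.5% and power of about 73-77% in the four assumed cases, against about 4.4% and 80-93% with participant and visit added. At zero between-visit correlation the literal test holds its 5%. At low correlation the added terms can cost power, so the gain is not guaranteed. The stated 80% is not tied to a within-participant test, and tests consistent with the wording differ by about 18-20 points for one assumed effect. Inflated false positives are not at issue, and the documents show neither an underpowered nor an adequately powered trial. All sizes depend on the assumed variance shares, effect pattern and correlations.

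**What to change.** **Section 13.1.** Add participant and visit number as factors alongside condition in the MANOVA of MEP amplitude, and name the test statistic. Make the fallback paired, for example by permuting condition labels within participant.

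**Optional and separate.** Use each visit's M1 as covariate, with M2 to M4 as responses. This gave about 85-95% power in the same cases and limits the loss when visits are weakly correlated. Say in either case that the omnibus condition test can respond to a tDCS after-effect already present at M2.

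**Sections 5.3 and 13.2.** Replace the per-arm sentence with the power for 16 completers under the named model, using the sponsor's own numeric effect size and a range of between-visit correlations that includes 0. The percentages given here should not be printed in the protocol, because they belong to assumed effects.

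**Cost.** Wording and one recalculation. Error df fall from 45 to 28, or 27 with M1. At zero correlation, power falls below the literal test by about 2 points with the M1 covariate (78 against 80%). Without it the loss is about 4 points (77 against 81%) or 9 points (71 against 80%), depending on the assumptions in step 5. N does not change, and the ceiling of 20 already allows 20−16 = 4 losses.

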14.6. N/A

14.7. We will follow all local and national regulations regarding the reporting of adverse events and serious adverse events.

15. Withdrawal of Subjects

- 15.1. *The PI may remove a subject from the study at any time if he/she believes that continuing is not in his/her best medical interests, or if he/she is unable to comply with the requirements of the study.*
- 15.2. *N/A*
- 15.3. *N/A*
- 15.4. *If a subject withdraws from the study, they will be asked if they would like to allow us to keep data that has already been collected. If they do not wish for this to happen, we will get rid of any CRFs by secured document-shredding methods and remove all data on that participant from our secured database.*
- 15.5. *The participant will need to speak with either the PI or research coordinator to verify they do not want to continue participating. There will be nothing in the consent to limit a participant from voluntary withdrawal.*

16. Data Management/Confidentiality

- 16.1. *Information and clinical data collected as part of this study will be labeled with the subject's initials and study number, which will be in a locked file cabinet in the PI's office that can be locked as well.*
- 16.2. *This research does not require direct identifiers such as name or address to be used.*
- 16.3. *This research does not require the access, use, or disclosure of Protected Health Information.*
- 16.4. *This research will ask about substance abuse as it is an exclusion criterion for this project, but we will not maintain any data or information with details about potential abuse.*
- 16.5. *We will not use a Certificate of Confidentiality to protect data.*
- 16.6. *Data (without identifiers) will be entered into a computer database and/or locked file cabinet in the PI's office. All computers with data will be password protected and databases will have no linking identifiers to the participant. All study team members have completed HIPAA training.*
- 16.7. *PI will be on-site at each study visit to ensure quality control standards are being met.*
- 16.8. *N/A*
- 16.9. *N/A*
- 16.10. *N/A*
- 16.11. *N/A*

17. Data and Specimen Banking

- 17.1. *N/A*

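### Section 15.4 lets a withdrawing participant have all CRFs and database data destroyed, with no exception for adverse events, stimulation received or withdrawal status

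*Combined protocol and SAP*

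**What the plan says.** Section 15.4 sets a two-step rule. On withdrawal, participants are first consulted: "they will be asked if they would like to allow us to keep data that has already been collected". If they decline, "we will get rid of any CRFs by secured document-shredding methods and remove all data on that participant from our secured database". The section lists no category of record that survives, and the protocol describes no separate withdrawal or safety log.

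Elsewhere the protocol commits itself on safety data:

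- Sections 7.2 and 14.2 say the study will collect expected side effects, namely "headache (expected 17% with transient headache that responds to simple analgesic) and nonspecific feelings of discomfort", and rare serious events such as seizure.
- Section 14.3: "The safety data will be reviewed on an ongoing basis during enrollment and conduct of the study".
- Section 14.7: "We will follow all local and national regulations regarding the reporting of adverse events and serious adverse events".
- Section 14.5 limits what is done with these data: "We have no planned formal analysis of the safety data".

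On numbers, section 5.2 states "We will aim to recruit 16 subjects for this study". Sections 5.3 and 13.2 ask for a ceiling of 20, to cover dropout and participants found after consent to meet an exclusion criterion.

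**The concern.** Ongoing review of safety data needs a cumulative record, and 15.4 allows part of that record to be removed at the request of someone who has left the study. A side effect is a plausible reason to leave, so the records removed may not be a random subset. With a target of 16, losing one or two participants visibly changes a count, and simple counts are all the safety output the plan provides for.

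Disposition is affected in the same way. If nothing is kept on a participant who was stimulated and then withdrew, the study data alone cannot show how many people were enrolled, how many received each condition, or how many left.

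**Working it through.** The plan computes no safety figure and states no dropout rate, so there is no figure of its own to reproduce. The check has two parts.

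**1. The sections side by side**

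| Section | Commitment | Compatible with deletion under 15.4? |
|---|---|---|
| 7.2, 14.2 | Collect headache, discomfort and serious events | Collected, but may then be erased |
| 14.3 | Review safety data throughout the study | Only until the request; later reviews would lack the record |
| 14.7 | Report adverse events as regulations require | A report may already be filed; nothing says the study's own record is kept |
| 15.4 | On refusal, destroy CRFs and remove all database data | States no exception |

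No section says which commitment prevails.

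**2. What deletion does to a count of this size (illustration)**

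Inputs: N = 16 (5.2) and a headache rate of 17% (7.2, 14.2). The number and pattern of deletions are assumed.

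- Expected headaches: 0.17 × 16 = 2.72, taken as 3. Full record: 3/16 = 18.8%.
- If k participants are erased, j of whom had a headache, the observed rate is (3 − j)/(16 − k).

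| Erased (k) | With headache (j) | Observed |
|---|---|---|
| 0 | 0 | 3/16 = 18.8% |
| 1 | 1 | 2/15 = 13.3% |
| 1 | 0 | 3/15 = 20.0% |
| 2 | 2 | 1/14 = 7.1% |
| 2 | 0 | 3/14 = 21.4% |

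If the one person erased is a random draw from the 16, the expected observed rate is (3/16)(2/15) + (13/16)(3/15) = 45/240 = 18.75%, the same as the full record. The rate is therefore biased downward only if withdrawal with refusal is more common among those with a headache. The loss of exposure and disposition information occurs either way, as does the loss of any event the erased person had.

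**The case against.** **No strict contradiction.** Collection, review and reporting can all take place before a later deletion request, and none of 7.2, 14.2, 14.3 or 14.7 promises retention. This stands in part: the sections are in tension and unreconciled rather than flatly contradictory. But 15.4 is an explicit instruction covering all data, so the problem is not mere silence.

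**Deletion is conditional and not wholly traceless.** It needs a withdrawal, a question and a refusal, and under 15.5 staff must speak with the participant. Section 15.4 names CRFs and database data, not signed consent forms or reports already filed under 14.7. This stands. A reader might infer that a serious event could disappear entirely. The documents do not support that: the PI is on site at every visit (16.7), a seizure would activate the hospital code team (section 9.3), and 14.7 would then apply. Such an event would probably be seen and reported before any shredding.

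**The size is assumed.** This also stands. A reader might infer that harm rates will be biased downward, for example from 19% to 7%. No document gives a withdrawal rate, a refusal rate or a link from headache to withdrawal, and headache is described as transient and responsive to simple analgesics. Sections 15.1 and 18.1 do allow participation to end for medical reasons or scalp redness, which makes a link plausible but does not quantify it. A reader might likewise infer that 4 of 20 recruits could be erased and replaced unnoticed, but that ceiling also covers exclusions found after consent, some of whom may never be stimulated.

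**The consequence is limited.** No formal safety analysis is planned. Exact 95% limits are wide and overlap heavily: 4.1% to 45.7% for 3/16 and 0.2% to 33.9% for 1/14. This limits the weight of the point, but is no reason to allow the only safety counts to be incomplete.

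**Participant choice and unseen consent wording.** Full erasure favours the participant's wishes, and the consent form, which is not in the reviewed text, may already limit deletion. If so, 15.4 should still say the same.

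**Conclusion.** The point holds for descriptive safety and disposition data. As written, 15.4 permits erasure of adverse-event, exposure and withdrawal records that the safety sections commit the study to collecting and reviewing. If the option is used, those counts will be incomplete. They will be biased downward only on the further assumption that withdrawal with refusal is related to a side effect. The size is unknown; the 2/15 and 1/14 figures are illustrations, not estimates.

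The point does not extend to the primary MEP comparison, which does not use these counts. Erased MEP data would leave that analysis too, but that is the participant's choice, which this point does not challenge. It is also unclear whether 15.4 applies to participants removed by the PI under 15.1; the revision should say.

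**What to change.** In section 15.4:

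- Limit the deletion option to excitability and behavioural data.
- State that the following are kept under the study number: allocated order, visits completed and stimulation received, withdrawal status, and all adverse-event records, serious or not.
- Commit to reporting the number withdrawn and the number with data deleted, by condition last received.
- Cross-refer to 14.2, 14.3 and 14.7, and say whether removals under 15.1 are handled the same way.

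Put matching wording in the consent form so that participants agree to the limit beforehand, subject to IRB agreement.

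The cost is a short addition to 15.4 and to the consent form. The small downside is that a withdrawing participant can no longer erase safety and disposition records. The right to withdraw and the choice over excitability and behavioural data are untouched, and 16.6 already provides for databases without linking identifiers. The change is best made before any request is acted on, because shredded records cannot be recovered.
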